6.2 FIDELITY

6.2.1 INTERVENTIONIST TRAINING AND TRACKING

We will assess fidelity in intervention delivery as follows:

- Enhanced usual care (WW™):
 - Per our data use agreement, WW™ has agreed to provide the study with the following process data: number of workshops attended (including dates of visits), workshop weights (if available), number of website or phone app logins (including dates and duration if available), and participant reported dietary and physical activity data.
 - At all study follow-up measurement visits (4, 12, and 24 months), research staff will carefully assess number, type, and duration of weight loss counseling sessions complete as part of the WW™ program.
- Med-South Weight Loss Program: We will assess fidelity of intervention delivery through multiple channels as describe below.
 - All counseling sessions will be logged into our REDCap data management program, including date and duration of visit.
 - After each visit, the counselor completes a checklist to indicate the components of counseling that were covered during the visit.
 - Audio recordings of up to 20% of sessions will be conducted during the 2-year period.
 - During Phase I and the early part of Phase II (first 2 months) a random 50% of the recorded counseling sessions will be reviewed and feedback provided to counselors. Recordings will be reviewed by study staff using a checklist to assess planned counseling components (accuracy of content covered and quality of delivery). If we find delivery fidelity is less than 80% of anticipated based on successful completion of counseling components, then the frequency of providing feedback to counselors from reviewed audio recordings will increase to ensure that the delivery fidelity goal has been achieved.
 - During the latter part of Phase II (last 6 months) and Phase III, audio recording will drop to 10% of visits (with review of up to 50% of recorded sessions), unless delivery fidelity is not achieved, in which the proportion reviewed will be increased to document achievement of fidelity goals.

6.3 MEASURES TO MINIMIZE BIAS: RANDOMIZATION AND BLINDING

Randomization

This is an open-label, randomized controlled trial of 360 participants desiring weight loss and followed over 24 months. Participants will be randomized 1:1, stratified by practice and diabetes status, to either:

- Group 1: Med-South Weight Loss Program (the intervention);
- Group 2: WW™ (Augmented usual care).

Randomized assignment will be done by using the randomization function in REDCap stratifying on site and diabetes status and using randomly permuted blocks of random sizes for the randomization to achieve balance in the participant allocation.

Unblinding Plan

As an open-label study, participants, providers, and many study staff will know to which group individual participants have been randomized. The investigative team, MPIs and Co-Is, (excluding the study statisticians [name] and [name]) will be blinded to group assignment of any

aggregated outcome data available before the completion of all data collection. Drs. [name] and [name] will not be blinded to study groups as their reports prepared for the DSMC will include unblinded data. Any key decisions by the study investigators (excluding the biostatisticians) regarding study outcomes, the appropriateness of test statistics or model assumptions, changes to this analysis plan, or any other statistical issues will be made in a masked review of the data (i.e., masked to the true randomization groups).

A randomization table (using randomly permuted blocks of random sizes for the randomization to achieve balance in the participant's allocation) will be prepared by the study statistician. This will be updated to the REDCap system by Drs. [name]. Only study biostatisticians will have access to this table. Outcome datasets provided to the statistician by the data management team will include the randomized arm assignment. Other study investigators will not have access to the primary outcome data until all data have been collected.

6.4 STUDY INTERVENTION/EXPERIMENTAL MANIPULATION ADHERENCE

Adherence to the intervention

- Twenty percent of counseling visits, selected at random, will be recorded and a subset of these reviewed to assess counselor adherence to the study protocol. In addition, the counselor will complete a brief questionnaire after each counseling session to record his/her observations about the process of the counseling session. This questionnaire will also be part of our assessment of fidelity.
- The extent to which participants perform weight management behavioral skills and cognitive strategies,¹³⁶ will be assessed from questionnaire data addressing self-monitoring of weighing, dietary behaviors, and goal-setting (instruments listed in the Measurement Table, Section 8.1.2).

6.5 CONCOMITANT THERAPY

Participation in this study does not preclude use of medications that are associated with weight loss.

FDA approved weight loss medication will be allowed in both intervention and usual care groups, if recommended by the participant's clinician. Similarly, medications for diabetes associated with weight loss (SGLT2 inhibitors and GLP1 agonists) may be used during this study. We will specifically address use of these medications at all measurement visits. If an imbalance in use occurs across study groups, we will account for this in our sensitivity analyses.

Bariatric Surgery

At enrollment, we assess interest in bariatric surgery and if a potential participant is contemplating this within the next year, he/she will not be enrolled. That said, a patient may elect to have bariatric surgery at any time during his/her participation in this study. If a participant has bariatric surgery, he/she will be withdrawn from the study at that time. Data collected prior to withdrawal will be included in the analysis.

6.5.1 RESCUE THERAPY

No rescue therapy outside of the study protocol is planned if participants do not lose weight.

7 STUDY INTERVENTION/EXPERIMENTAL MANIPULATION DISCONTINUATION AND PARTICIPANT DISCONTINUATION/WITHDRAWAL

7.1 DISCONTINUATION OF STUDY INTERVENTION/EXPERIMENTAL MANIPULATION

The study intervention will not be discontinued unless the participant withdraws or is withdrawn as outlined in the above section.

If a participant withdraws or is withdrawn, no attempts will be made to collect follow-up measures.

If a participant requests to withdraw from the intervention but is willing to continue the measurement component of the study, he/she will be invited to continue with follow-up measures.

7.2 PARTICIPANT DISCONTINUATION/WITHDRAWAL FROM THE STUDY

Participants are free to withdraw from participation in the study at any time upon request.

Participants will be withdrawn according to protocol for the following reasons:

- New diagnosis of condition on study entry exclusion criteria list (type 1 diabetes and cancer, as defined on the list).
- Other medical diagnosis typically associated with significant weight loss (5% or more of body weight). In addition to malignancy, examples include nonmalignant gastrointestinal disease, endocrinopathies, infectious disease, rheumatologic diseases, etc. As [name] (study Co-I, general internist) will be blinded to participants' study group assignment, he will adjudicate in these situations, seeking consultation from medical colleagues as appropriate.
- New diagnosis of cognitive decline confirmed by PCP as sufficient to interfere with insight related to food selection.
- New diagnosis of medical condition such that participation in a behavioral weight loss intervention is no longer appropriate.
- Permanent change in living situation (e.g. from home to nursing home) such that the participant has limited food options.

Pregnancy: Study participants who become pregnant may continue to participate in the study with the understanding that weight loss goals will be suspended during pregnancy through 3 months postpartum. If a pregnant participant wishes to continue with counseling session during pregnancy, the focus on counseling will be on dietary quality. The participant may resume full participation 3 months postpartum. Any data collected while the participant is pregnant will be censored and follow-up data will not be collected until the participant is 6 months postpartum.

A participant will be considered lost to follow-up if we are unable to contact him/her according to this algorithm.

- Attempts at telephone contact:

- We will call up to 5 times over a 2 week period. We will attempt 2 calls during regular work hours (8:30 to 5:30 on weekdays) and 3 after hours, including Mon-Thurs evening between 5:31 and 9:00 pm and on Saturday calling between 8:30 and 5:30 pm.
- We will leave up to 2 phone messages.
- If no contact is made over this initial 2 week period as outlined above, we will undertake more limited contact attempts for an additional 2 weeks including up to 2 phone calls per week, 1 during business and the other during evening hours or on the weekend.
- Email: If a participant gives us permission to contact by email, we will send up to 4 weekly emails.
- Text: If a participant gives us permission to contact by text, we will send up to 4 weekly texts.
- Alternative contact: During enrollment, we will collect information on an alternative contact that we are given permission to contact. We will attempt to contact this individual up to 3 times a week for 4 weeks.

No replacement is planned for those who withdraw from the intervention for the study.

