8.3.2 DEFINITION OF SERIOUS ADVERSE EVENTS

For this study a serious adverse event includes, as outlined at: <https://www.hhs.gov/ohrp/regulations-and-policy/guidance/reviewing-unanticipated-problems/index.html>:

1. results in death;
2. is life-threatening (places the subject at immediate risk of death from the event as it occurred);
3. results in inpatient hospitalization or prolongation of existing hospitalization;
4. results in a persistent or significant disability/incapacity;
5. results in a congenital anomaly/birth defect; or
6. based upon appropriate medical judgment, may jeopardize the subject’s health and may require medical or surgical intervention to prevent one of the other outcomes listed in this definition (examples of such events include allergic bronchospasm requiring intensive treatment in the emergency room or at home, blood dyscrasias or convulsions that do not result in inpatient hospitalization, or the development of drug dependency or drug abuse)

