8.3.4 TIME PERIOD AND FREQUENCY FOR EVENT ASSESSMENT AND FOLLOW-UP

Solicited potential adverse events will occur at each follow-up measurement visit (4, 12, and 24 months). They include the following and we will ask if evaluation for these events included emergency room visit or overnight hospital stay.

- Acute myocardial infarction
- Angina pectoris
- Stroke
 - Thrombotic
 - Hemorrhagic
- TIA
- Heart failure
- Coronary bypass surgery
- Cancer
 - Type of cancer
- Broken bone
 - Type of fracture
- Light headedness or dizziness
- Pneumonia
- Other infection
 - UTI
 - Other
- Hypoglycemia
 - Other

As allowed by our HIPAA authorization, the EHR will be reviewed to confirm the above events and modify the date of occurrence if not accurately provided by the participant. For clinical events that were managed outside of facilities with EHR data available to investigators, we will request that participants sign a release of medical information so that pertinent medical records can be reviewed.

Unsolicited adverse events (AE) or serious adverse events (SAE) may come to the attention of study staff during counseling visits, phone calls, or via other channels of communications. They will be categorized as above and entered into the appropriate follow-up questionnaire at the time of occurrence.

Information to be collected about AEs and SAEs includes event description, time of onset, study clinician's assessment of severity, relationship to study procedures (assessed only by those with the training and authority to make a diagnosis), and time of resolution/stabilization of the event. All AEs occurring while on study will be documented appropriately regardless of relationship. All AEs will be followed to adequate resolution.

Any medical or psychiatric condition that is present at the time that the participant is screened will be considered as baseline and not reported as an AE. However, if the study participant's condition deteriorates at any time during the study, it will be recorded as an AE.

Changes in the severity of an AE will be documented to allow an assessment of the duration of the event at each level of severity to be performed. Documentation of onset and duration of each episode will be maintained for AEs characterized as intermittent.

Study staff will record events with start dates occurring any time after informed consent is obtained until the last day of study participation.

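### The pregnancy rule in Protocol 7.2 and 8.3.9 is not limited to weight and efficacy data, so as written it conflicts with the requirement to record every adverse event on study

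*Protocol*

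**What the plan says.** - **Protocol 7.2, pregnancy paragraph.** "Study participants who become pregnant may continue to participate in the study", with weight loss goals suspended and counseling available on diet quality. Then: "Any data collected while the participant is pregnant will be censored and follow-up data will not be collected" until 6 months postpartum. Full participation may resume 3 months postpartum.
- **Protocol 8.3.9, Reporting of Pregnancy.** The same paragraph again, inside the adverse event chapter. It adds no exception for safety data.
- **Protocol 8.3.4.** "All AEs occurring while on study will be documented appropriately regardless of relationship". Also: "Study staff will record events with start dates occurring any time after informed consent is obtained until the last day of study participation". Pregnancy is not mentioned.
- **Protocol 8.3.4 and the measures table in 8.1.2.** Solicited events are tied to the measurement visits: "Solicited potential adverse events will occur at each follow-up measurement visit (4, 12, and 24 months". The measures table lists adverse outcomes, cardiovascular events, emergency visits and hospital stays as collected at follow-up only.
- **SAP 6.1 and 9.5.** Safety is summarized by group in all randomized participants. The SAP contains no pregnancy rule.

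**The concern.** Weight measured in pregnancy does not reflect the diet program, so removing it from the efficacy analysis is reasonable. The wording goes further: it covers data of every kind and stops all follow-up collection, yet the participant stays in the trial and may keep receiving counseling. Full participation can restart 3 months postpartum but collection only at 6, which leaves 6 − 3 = 3 months of possible full intervention with follow-up collection still paused.

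Staff who apply 7.2 literally would not ask the solicited safety questions. An analyst who applies it literally would drop events recorded during pregnancy from the safety tables while keeping the participant in the denominator. Staff and analysts who follow 8.3.4 would do the opposite. The documents do not say which section governs.

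**Working it through.** The plan gives no figure to reproduce. The check compares the sections and then asks which visits the rule can reach.

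**Step 1. Does the rule reach safety data?**

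| Question | Pregnancy rule (Protocol 7.2, 8.3.9) | Elsewhere |
|---|---|---|
| Which data are censored? | All data collected in pregnancy | SAP 6.3: outcome data only. SAP 6.4: weight change data only |
| Which collection stops? | Follow-up data, until 6 months postpartum | Measures table: adverse outcomes are a follow-up item |
| Are adverse events excepted? | No | 8.3.4: every event from consent onward, with no pregnancy exception |

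The two halves of the rule act differently. The stop in collection conflicts directly with 8.3.4, because the solicited questions are part of follow-up. The censoring does not stop anything being recorded, but it could take recorded events out of the tables in Protocol 9.4.4 and SAP 9.5.

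**Step 2. Which solicited visits can be affected?** The documents give no length of pregnancy, so assume 9 months, with 2 months as a low case for one that ends early. Let c be the month of conception after randomization and S the length of the rule's effect.

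- S = 9 + 6 = 15 months; low case S = 2 + 6 = 8 months.
- A visit with window a to b is wholly covered when c ≤ a and c + S ≥ b, that is, when b − S ≤ c ≤ a.

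| Visit | Window in Protocol 1.3 (months) | Covered if S = 15 | Covered if S = 8 |
|---|---|---|---|
| 4-month | 3 to 8 | c from 0 to 3 | c from 0 to 3 |
| 12-month | 11 to 18 | c from 3 to 11 | c from 10 to 11 |
| 24-month | 23 to 30 | c from 15 to 23 | c from 22 to 23 |

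The wider SAP 5.4 windows end at 596/30.4 = 19.6 and 954/30.4 = 31.4 months. With S = 15 the lower bounds on c become 19.6 − 15 = 4.6 and 31.4 − 15 = 16.4 months. With S = 8 neither window can be wholly covered, since they last (596 − 335)/30.4 = 8.6 and (954 − 700)/30.4 = 8.4 months.

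A missed 4- or 12-month questionnaire is a delay if a later one asks about the same period; the documents do not state the recall period. A missed 24-month questionnaire has no later visit behind it, because Protocol 4.4 ends the study there.

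**Step 3. Effect on the tables.** Each arm has 360/2 = 180 participants. One participant whose only event of a given type is left out changes that arm's percentage by 1/180 = 0.56 points.

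**The case against.** The strongest reply is that the sentence was meant for weight. It closes a paragraph on suspended weight loss goals, it does not name adverse events, and the SAP applies censoring only to outcomes. That is probably the intent. It is not what the text says, and placing the same sentence in 8.3.9 as the pregnancy reporting rule makes a weight-only reading less secure.

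The second reply is that other routes stay open. Under 8.3.4, unsolicited events from counseling, calls and other contacts are entered as they occur. Protocol 8.3.5 keeps expedited and monthly reporting, and the DSMC charter in 10.1.6 has the team monitor deaths, hospital stays and emergency visits; none of these excludes pregnancy. This stands, and it limits the loss mainly to solicited events. Study counseling, one of these routes, is given only to the Med-South arm, so the safeguard may not be equal across arms.

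The third reply is that the SAP safety tables contain no pregnancy exclusion. That also stands. Removal of recorded events would follow from applying the Protocol wording to the tables; the SAP does not state it.

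Four stronger readings may occur to a reader, and the documents do not support them:

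- **The plan chose to discard safety data.** No section says so. What is missing is a limit on scope.
- **The rule empties the serious-event criterion "results in a congenital anomaly/birth defect".** An anomaly found at or after birth is not data collected during pregnancy, and it can be reported unsolicited or when collection resumes.
- **The participant would appear event-free.** Events before conception and after 6 months postpartum remain, as may unsolicited ones.
- **15 of 24 months (63%) would have no safety data.** This is a worst case. It assumes a full-term pregnancy wholly within the 24 months and silence from every unsolicited route.

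**Conclusion.** The point holds as a conflict of wording with a limited effect. Read literally, 7.2 and 8.3.9 pause the solicited safety questions and allow recorded events to be censored, while 8.3.4 requires all events to be documented. The sections need to be reconciled.

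The practical size is small. Protocol 5.2 screens out women up to age 50 who are pregnant, breastfeeding or planning pregnancy within a year, so few participants are likely to be affected, although pregnancies planned for the second year are not screened out and no count is given. The safety summaries are descriptive, and the primary weight comparison is little changed. The conclusion rests on the plain wording; the visit timings in the working rest on the assumed length of pregnancy and on the visit windows being enforced. The change is still worth making because it costs almost nothing and removes a rule that could drop safety data.

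**What to change.** 1. In Protocol 7.2 and 8.3.9, limit both the censoring and the pause in collection to weight and other efficacy measures, in the way SAP 6.3 and 6.4 already limit theirs. State that 8.3.4 continues to apply.
2. In SAP 9.5, state that adverse events, emergency visits and hospital stays during pregnancy and the 6 months postpartum are retained in the by-group tables.
3. For any participant whose solicited questions were skipped under the rule, look for the missed events in the EHR review provided for in 8.3.4. That section describes the review as confirming events and dates, so add a line saying it is also used for this purpose.

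The cost is a few sentences in each document and a chart check for the few participants concerned. The SAP was drafted after all participants were randomized, and SAP 9.4.1 notes that the analysis was being reviewed in May 2025, so this is a clarification and a retrospective check. New postpartum questionnaires or a separate pregnancy-outcome follow-up are not needed.

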7.3 LOST TO FOLLOW-UP

A participant will be considered lost to follow-up if we are unable to contact him/her according to this algorithm.

- Telephone contact:
 - We will call up to 5 times over a 2 week period. We will attempt 2 calls during regular work hours (8:30 to 5:30 on weekdays) and 3 after hours, including Mon-Thurs evening between 5:31 and 9:00 pm and on Saturday calling between 8:30 and 5:30 pm.
 - We will leave up to 2 phone messages.
 - If no contact is made over this initial 2 week period as outlined above, we will undertake more limited contact attempts for an additional 2 weeks including up to 2 phone calls per week, 1 during business and the other during evening hours or on the weekend.
- Email: If a participant gives us permission to contact by email, we will send up to 4 weekly emails.
- Text: If a participant gives us permission to contact by text, we will send up to 4 weekly texts.
- Alternative contact: During enrollment, we will collect information on an alternative contact that we are given permission to contact. We will attempt to contact this individual up to 3 times a week for 4 weeks.

If we are unable to contact a participant as outlined above, a letter will be sent to the current mailing address in the EHR outlining our attempts to contact the participant and inviting the participant to contact us if he/she still wishes to participate in this study.

Should the participant continue to be unreachable and does not respond to the mailed letter within 4 weeks, he or she will be considered to have withdrawn from the study with a primary reason of lost to follow-up.

8 STUDY ASSESSMENTS AND PROCEDURES

8.1 ENDPOINT AND OTHER NON-SAFETY ASSESSMENTS

8.1.1: Screening, eligibility assessment, and consent

- Outlined in detail in Section 5.5, Strategies for Recruitment and Retention.

8.1.2: Overview of study measures

Study data will be collected at baseline, 4, 12, and 24 months. Process data for the intervention group (Med-South Weight Loss Program) will be collected as part of the intervention via the web-based platform and via REDCap questionnaires completed by counselors immediately after counseling sessions. Process data for the enhanced usual care group will be assessed via a Data Use Agreement with WW™ and by questionnaire at follow-up visits. *As recommended by NIH, our measures include ADOP^T¹³⁷⁻¹³⁹ core constructs (in blue) and specific instruments (in blue underlined) as noted in the Table.*

Primary and Secondary Aims 1 and 2:

Table 3: Outcomes/ Measures	Collection Time (min)	Data collected times (months)				Comment
		0	4	12	24	
Weight (primary outcome) , by electronic scale as the average of two measures, and height (baseline only). SECA 874 dr scales will be used and assessed monthly for accuracy with standardized weights..	5	x	x	x	x	At study outset, seven standardized 50 lb. weights certified for accuracy by NC state standards lab.*
Secondary Outcomes						
Objective measures						
--Blood pressure by noninvasive automated monitor (Omron HEM-907XL, Vernon Hills, IL) with a first measure after seated for 5 minutes and 2 repeat measures at 1-minute intervals	10	x	x	x	x	
--Blood work: performed by LabCorp 
Fasting lipid panel: total cholesterol, triglycerides, HDL, and calculated LDL and VLDL. If participants are unable to fast a non-fasting sample is collected with non-fasting stat notedA1cOther chemistry: glucose, ALT, creatinine (if not previously checked in prior 2 years and only at baseline), and CRP	10	x	x	x	x	Creatinine collected at baseline for those without measure in preceding 2 years.

--blood work: preformed in lab of [name]. Serum and plasm specimens are frozen to – 80 C. immediately after collection and processing. • interleukin (IL)-6, tumor necrosis factor (TNF)-alpha, and C-reactive protein (C-RP)						
--skin carotenoids, Reflection Spectroscopy Device ("Veggie Meter"™) ¹⁴⁰⁻¹⁴²	5	x	x	x	x	
Questionnaires:						These data collected before the actual visit, on-line via REDCap or by phone. Window before baseline visit is 4 weeks. Window before follow-up and after follow-up visits is 2 weeks.
--Demographics and medical history (baseline only)	15	x				
--Diet assessment: diet quality, ¹⁴³ adapted PREDIMED checklist ^{19, 96}	10	x	x	x	x	
--Detailed assessment of diet quality: Willett Food Frequency Questionnaire ¹⁴⁴	20-30	x	x	x	x	
--Physical activity and sedentary behaviors: GPAQ for physical activity and sedentary behavior , ¹⁴⁵ participant report of monitored steps	5	x	x	x	x	
--Quality of life (EQ5D ¹⁴⁶)	5	x	x	x	x	
--Food insecurity ¹⁴⁷	2	x	x	x	x	
Diet Self-Efficacy Scale ¹⁴⁸	3	x	x	x	x	
Weight Loss Self-efficacy Short-Form (WEL-SF1) ^{149, 150}	3	x	x	x	x	
Early Self-Weighing Questionnaire ¹⁵¹	1	x	x	x	x	
Self-Regulation: Dietary Self-Regulation (TSRQ) ¹⁵²	3	x	x	x	x	
Three-Factor Eating Questionnaire ¹⁵³	3	x	x	x	x	
Mindful Eating Questionnaire ¹⁵⁴ **	5	x	x	x	x	

Perceived Stress Scale ¹⁵⁵	3	x	x	x	x	
PHQ-8 ¹⁵⁶	3	x	x	x	x	
--Medications for high BP, high blood lipids, diabetes, and weight loss (self-report with EHR review)	5	x	x	x	x	
--Adverse outcomes, CVD events, ER visits, and hospitalizations (follow-up only)	5		x	x	x	
--Acceptability (follow-up only)	5-10		x	x	x	
Diet and PA goals and success achieving goals (collected by web-based intervention platform and counselor)	NA					Collected after each counseling session in intervention group.
Exploratory Outcome						
Stool microbiome (participants may elect not to complete this measure)	NA	x	x	x	x	First sample will be collected in the 2 week period immediately after randomization. (These are the only baseline data collected after randomization.) The follow-up samples will be collected w/n a 2 week window of follow-up visit date.
Other						
--EHR to assess/confirm adverse health outcomes	NA		x	x	x	To confirm information collected by questionnaire at these visit time points

* <http://www.ncagr.gov/standard/Labs/>

**Added to baseline on 12/22/20. No follow-up data had been collected at this point in the study.

Note: table last updated 3/1/21

Additional Study measures—economic outcomes

The budgetary impact assessment and numerator for the cost effectiveness analysis will be based on Activity Based Costing Questionnaires previously developed and applied by [name] in similar studies^{99, 157} along with participants' health care claims data that will be used to compare resource

utilization between the intervention and control groups. The denominator for the cost effectiveness analysis will focus on weight loss (kg) and health related quality of life as assessed using the EQ-5D-5L.¹⁴⁶

8.1.3: Detailed protocol for data collection

8.1.3a: Protocol Updated 3/16/21: Study visits after hospitalization.

- Enrollment and follow-up measurement visits:
 - May occur 2 or more weeks after hospital stay if less than 7 days (defined as 2-7 nights in the hospital).
 - May occur 30 or more days after hospital stay of more than 7 days (defined as 8 or more nights in the hospital).
 - Note: ER visits and 1 night in the hospital (often defined as observation) do not count as hospitalization.
- Counseling sessions:
 - No interval specified. To be determined by counselor and participant.

Note: Research staff will be trained and periodically retrained on data collection protocols. Baseline training will include detailed review of and practice with protocols under the direction of the study's MPIs, Study Manager, and Data Manager. Retraining will occur at quarterly intervals.

8.1.3.1: Weight and height protocols

- At study outset, weights (seven 50 pound weights) assessed and adjusted for accuracy on 12/3/19 by North Carolina Department of Agriculture and Consumer Services Standards Laboratory.
- Weights to be re-assessed and adjusted for accuracy annually.
- Scales tested for accuracy the first week of each month during their use in this study.

Seca 874 dr Scale Tolerance Testing (updated 1/28/20)

The scale's 6 AA batteries should be replaced at least once a year.

It is **imperative** that tolerance weights be handled carefully (no slamming around or banging against one another) to maintain their accuracy.

Before starting the test set the **ON-OFF** switch to **ON**. Press the **start** key with no load on the scale. If necessary switch the weight display from **kg** to **lbs** by pressing the **2 in 1** key for approximately 3 seconds.

- 1) Place a 50 lb wt in the center of the scale and record weight. (~50 lbs) Remove the 50 lb wt. Press **start** key.
- 2) Carefully stack two 50 lb wts on top of one another in the center of the scale. The first weight must be gently vibrated until the second is in place to prevent the scale from prematurely locking in and giving an erroneous reading. Record the weight reading (~ 100 lbs). Press the **2 in 1** key.

3) Place a third 50 lb wt on the scale and record weight. (~50 lbs The sum of this weight and the weight observed in step 2, ~ 100 lbs, is the observed reading for the expected weight of 150 lbs) **Remove the top 50 lb wt. only.**

4) Place two 50 lb wts on top of the two remaining weights vibrating the stack as before. Record the weight reading (~ 100 lbs The sum of this weight and the weight observed in step 2, ~ 100 lbs, is the observed reading for the expected weight of 200 lbs). Remove all four weights. Press **start** key.

5) Carefully, but quickly, stack five 50 lb wts on top of one another in the center of the scale, gently but firmly vibrating the stack until the fifth weight is added. Record the weight reading (~ 250 lbs). Press the **2 in 1** key.

6) Place a sixth 50 lb wt on the scale and record weight. (~50 lbs The sum of this weight and the weight observed in step 6, ~ 250 lbs, is the observed reading for the expected weight of 300 lbs) **Remove the top 50 lb wt. only.**

7) Place two 50 lb wts on top of the five remaining weights vibrating the stack as before. Record the weight reading (~ 100 lbs The sum of this weight and the weight observed in step 6, ~ 250 lbs, is the observed reading for the expected weight of 350 lbs). Remove all weights.

8) Set **ON-OFF** switch to **OFF**.

During the testing if any observed reading falls outside the tolerance range repeat the testing steps to verify the reading. No need to continue testing the scale if a weight is out of range and verified. Scales failing the tolerance testing should no longer be used.

lbs	0.40%	
	Tolerance	
	Limit	Range
50	0.2	49.8 - 50.2
100	0.4	99.6 - 100.4
150	0.6	149.4 – 150.6
200	0.8	199.2 – 200.8
250	1	249.0 – 251.0
300	1.2	298.8 – 301.2
350	1.4	348.6 – 351.4

Scale S/N _____

Date _____

Expected Weight (lbs.)	Observed Weight (lbs.)	Difference (lbs.)	0.40% Tolerance Limit (lbs.)
50	_____	_____	0.2
100	_____	_____	0.4
(50)	_____	_____	
150	_____	_____	0.6
(100)	_____	_____	
200	_____	_____	0.8
250	_____	_____	1
(50)	_____	_____	
300	_____	_____	1.2
(100)	_____	_____	
350	_____	_____	1.4

WEIGHT MEASUREMENT PROTOCOL

(last updated 10/28/19)

Prior to the appointment the participant is instructed to wear light clothing and informed that the weight measurements will be made with shoes removed.

Materials

- Seca model 874 dr electronic personal scale

Preparation

- Place the scale on a hard level surface.
- Turn the scale ON with the ON-OFF switch. Press the start key with no load on the scale. The scale is automatically set to zero and ready for use.
- Once the digital display reads zero **verify that “lbs” unit is showing**. If “kg” appears in the display press the 2 in 1 key for approximately 3 seconds. “lbs” should then show in the display.

Procedure

Participant

- With shoes removed, scale displaying zero; step onto the middle of the scale.
- Stand on both feet, knees extended (straight) with arms by sides.

Research Staff

- Once the reading in the digital display is stable, record the first weight on the Weight Measurement Form in lbs, **recording the tenths of lb** (i.e. 81.4 lbs).
- Have the participant step off the scale.
- Have the participant step back onto the scale once zero is displayed. **Note:** You may need to restart the scale by pressing the start key to obtain the zero and lbs display before instructing the participant to step back onto the scale.
- Once the reading in the digital display is stable, record the second weight on the form.
- Record the difference between the first and second readings.
- If the **difference is greater than 1 lb repeat** and record a third weight.
- When finished weighing participants turn the scale OFF with ON-OFF switch.

Note

- A stabilized reading in the scale display is needed for recording. The participant needs to stand very still while breathing naturally. If moving too much the weight will not stabilize in the display.

Scale Accuracy Testing

- To insure accuracy the scales have been tested using certified tolerance weights. (Performed by research center staff each month).
- Staff should weigh themselves whenever the scale is set up for participant measurement

Scale Care

- Treat the scale as a laptop. Do not bump against other objects or expose to extreme temperatures.
- Store in the horizontal position without stacking anything on top.
- Do not allow anyone to weigh without your supervision and instructions.
- When not using, turn the ON-OFF switch to OFF to conserve the battery.

8.1.3.2: Height Protocol

HEIGHT PROTOCOL *(last updated 1/28/20)*

Prior to the appointment the participant is instructed to wear light clothing and informed that both height and weight measurements will be made with shoes off.

Materials

- Shorr infant/child/adult stadiometer

Procedure

Participant

- Shoes removed.
- Back to the height board, heels all the way to the back.
- Standing up straight with arms by sides (**Evaluate posture** to be sure participant is standing upright, flat-footed and looking straight ahead with head in the Frankfort horizontal plane, the horizontal plane which includes the lower margin of the bony orbit--the bony socket containing the eye--the most forward point in the supratragal notch--the notch just above the anterior cartilaginous projections of the external ear). See “Frankfort Plane for Measuring Body Height” diagram.

[figure not shown]
9 Research Staff

- Lower the sliding headpiece onto the participant’s head.
- Read the measuring scale of the stadiometer to the **nearest 1/8th inch** (Note: stadiometer is scaled in inches, not centimeters).
- Two measures are taken and recorded on REDCap form. The participant steps off the stadiometer between measures. If the two measures **differ by >1/4 inch a third measure is taken** and recorded in the “blank” for the 3rd observation.
- Height is determined from the 2-3 observations (the average of the 2 closest measurements, **rounding up to nearest 1/8th inch**) and recorded on the form.
- Record your staff ID number on the REDcap form.

Notes:

- If the participant is breathing heavily enough to cause oscillations in the sliding headpiece, you must wait until s/he has settled down or ask to exhale and hold breath.
- If the participant’s hairstyle interferes with measurement, be flexible and creative and get an accurate measurement (i.e. remove ponytail holders, measure hair height with tape measure, flatten hairdo, etc.).
- If the participant’s buttocks cause an irregular or very unnatural posture when the heels are against the back of the board, allow standing with feet under hips (heels will not be against the back of the board in this case).

Frankfort Plane for Measuring Body Height

ORBITALE: Lower margin of eye socket

TRAGION: Notch above tragus of ear or at upper margin of zygomatic bone at that point

FRANKFORT PLANE: Orbitale-tragion line horizontal

8.1.3.2: Blood pressure protocol

BLOOD PRESSURE PROTOCOL (updated 1/28/20)

Warnings

- Do not share an electric outlet with another unit or electric appliance.
- Keep unit at least 5 feet from cell phones and computers.
- Unplug AC adaptor from electric outlet if unit is unused for an extended period of time.
- Do not inflate the cuff without being wrapped over the arm.
- Do not store unit under high temperature and high humidity.
- Transport the unit inside a car, not in the trunk.

Materials

- Omron Model HEM-907XL blood pressure monitor with small, medium, large, and extra large cuffs
- Tape measure

Note: The Omron cannot be used on arms with a circumference greater than 17" (large Omron cuff does not fit) or if the Omron is unable to take the measurement.

Procedure using the Omron

Set up

- Connect the AC adapter to the DC jack of the main unit and the electric outlet.
- Connect the air tube to the main unit by securing the air plug to the base of the air connector. This air tube is for use with the small, medium, and large cuffs only. The extra large cuff has its own non-detachable air tube for connection to the main unit.

Participant

- Should avoid caffeine, exercise, and smoking for at least 30 min before measurement.
- Invite participant to empty bladder before measurement .
- Shirt, blouse, or dress sleeves are loose fitting enough not to cause constriction of the arm even when pushed up for wrapping the cuff onto the bare arm. If too tight, the arm needs to be placed outside the sleeve.
- Remains quietly seated in a chair with both feet flat on the floor and back supported while measurements are taken. Neither the participant nor the staff should talk during the 5 min rest period or during the measurement.

Research Staff

- Apply the cuff to the right arm of the seated participant. **All BP measurements are made using the right arm unless prevented by injury or deformity.** If the left arm is used it is indicated on the BP and Heart Rate (BPHR) form and subsequent BP measures are taken using the left arm. See "How to Apply the Cuff" diagram.

- Measure the circumference of the largest part of the upper arm and select the cuff according to arm size.
 - ◀ 7"-9" small
 - ◀ 9"-13" medium
 - ◀ 13"-17" large
 - ◀ 17"- 20" extra large
- Connect the air tube and the cuff/bladder set by rotating the Luer connection.
- Place the participant's hand with the palm upward.
- Align the Artery Position Mark on the cuff with the brachial artery.
- Wrap the cuff snugly using both hands and securely fasten it with the Velcro™ tape. **The lower edge of the cuff should be placed ½" to 1" above the inner side of the elbow joint.**
